#### Feasibility outcomes

##### 1. Recruitment:

We will record the number of clinicians and eligible service users who were approached and agreed to take part.

##### 2. Retention:

We will record the number of clinicians and service users who dropped out of the study and reasons, and the number of participants that complete the follow-up assessment.

##### 3. Adherence:

We will examine data on how many sessions were delivered and reasons for sessions being missed.

##### 4. Fidelity:

All the sessions will be audiotaped (and videotaped using Microsoft Teams if possible) and 20% of the recordings for each clinician will be selected randomly and rated using a fidelity checklist to identify the extent to which the intervention was delivered as intended. We will also review 20% of the action plans. The fidelity checklist will be adapted from the checklist developed for the DIALOG+ trial in people with psychosis.

##### 5. Acceptability:

Semi-structured interviews will be held with 6-10 clinicians, 10 service users and 10 participant carers supporting service users. We will use purposive sampling to identify service users who received at least half the sessions (3 or more), and those who received less than half the sessions (0-2 sessions) and we will interview clinicians from different backgrounds, and paid and family participant carers, in order to obtain a range of perspectives. Clinicians will be asked about their perspectives on the quality of training and supervision received, views about the ease of using the app and technical challenges and practical and organisational issues (e.g. time, resources) in implementing aDIALOG+. Topic guides for the service users will be developed with input from the PPI advisory group. The questions will include views about the accessibility and ease of using the app, perceived

benefits and unintended consequences of aDIALOG+, and aspects that did or did not work well and suggestions for improvements/changes. The interviews will be held after the collection of outcome data and will be conducted by a research assistant not involved in the collection of outcome data. The interviews will be audiotaped and transcribed verbatim using an approved transcription company. We will also ask clinicians to complete the NoMAD questionnaire (39) for assessing implementation processes from the perspective of professionals directly involved in the work of implementing complex interventions in healthcare.

## 6. Completion of outcome measures:

Assessments will be conducted at baseline and post intervention (6 months) by the research assistants or CSOs and will take place face-to-face or conducted remotely (telephone or videoconference depending on preference). Outcomes will be assessed in both service users and participant carers. We will examine the proportion of participants who complete the following outcomes:

### Outcomes in service users

#### i. Behaviour that challenges

Changes in behaviour will be measured using the Aberrant Behaviour Checklist (ABC)-Irritability subscale (43). This is one of the five domains of the Aberrant Behaviour Checklist-Community (ABC-Community) and comprises 15 items rated on a 4-point Likert scale (0=never a problem; 3=severe problem). This will be completed by participant carers.

#### ii. Quality of life

Changes in quality of life will be measured using the 13- item WHOQOL Disabilities module (WHOQOL-DIS) (40) which will be completed with service users and has been validated in people with ID.

#### iii. Community participation

Community and Leisure participation will be measured using the Guernsey Community Participation and Leisure Assessment – Revised (GCPLA-R), a 23 item scale developed for use in people with ID (44). This will be completed by participant carers.

#### iv. Psychological distress

Changes in psychological distress will be measured using the Learning Disability – Clinical Outcomes in Routine Evaluation, 14 item version (LD-CORE-14) (42), which will be completed with service users.

#### v. Psychiatric disorders

We will assess changes in the presence of psychiatric disorders using the Moss Psychiatric Assessment Schedule - Check (Moss-PAS Check) (45), which provides scores relating to anxiety, depression, elevated mood and hyperactivity, obsessive compulsive disorder, psychosis and possible organic disorder in people with ID. This will be completed by participant carers.

#### vi. Global improvement

We will assess whether there are changes in behaviour and functioning as a result of the intervention (at 6 months) using a modified version of the Clinical Global Impressions Scale

(CGI) (46). The CGI global improvement measure (CGI-I) will be rated by the clinician (or care worker) delivering aDIALOG+, the service user and also the participant carer. The scale is rated from 1 (very much improved) to 7 (very much worse).

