### 3. Work package 2: A feasibility study of delivering aDIALOG+ in clinical services

We will conduct a single arm, uncontrolled, feasibility study of aDIALOG+ delivered by new (haven't participated in other work packages) clinicians from community ID services to assess recruitment and retention of service users and clinicians. We will recruit 8-12 clinicians, who will be eligible if they are aged 18 or over, are currently working within a community ID service, intensive support team or in a local authority or social care organisation for people with ID, are from any profession (e.g. psychology, nursing, speech and language therapy, psychiatry, social work) at grade 4 and above with a minimum of six months experience working with people with ID, consent to participate and haven't participated in other work packages.

Clinicians will administer aDIALOG+ to 3-5 service users with ID on their caseload (30 service users in total), and they will be identified through the review of medical records. Service users and their carers will then be approached by the participating clinician or CSO to take part in the study and an information sheet will be provided. Service users will be eligible if they are aged 18 or over, have mild or moderate ID based on service records / clinical notes, have a current history of behaviour that challenges (at least one incident of self-injurious behaviour, physical aggression or damage to property in the last 3 months), are living in any setting including the family home and supported living/ residential home, and can provide informed verbal or written consent. Participant carers will be eligible if they are aged 18 or over, are paid or unpaid (e.g. family carer); if a paid carer, they will need to have worked with the person for at least six months and should know the person well and support the person on a regular basis, and consent to participate. We will ask clinicians to identify and approach all the service users on their caseload, who are potentially eligible to take part, to take part in the study until they reach the recruitment target. This should reduce the likelihood of clinicians only approaching certain individuals to take part.

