#### 4. Work package 3: A feasibility study of aDIALOG+ in care homes

We will conduct a single arm, uncontrolled study of aDIALOG+ delivered by new (haven't participated in other work packages) care workers from care homes (supported living or residential care) for people with ID. The main aim of this study is to explore the recruitment and retention of care homes, care workers and service users, the acceptability, adherence and fidelity of aDIALOG+ delivered by care workers and completion of outcome measures. We will recruit ten care homes and their paid staff (approximately three to five staff in each care home) from East London, Bedfordshire and Cornwall. Care homes will be identified from Care Quality Commission websites and local authority and national registers. We will also use the ENRICH network (Enabling Research in Care homes) to identify care homes that are interested in research.

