In order to determine the minimal clinically important difference (MCID) for our primary outcome measure (ABC-I), we will compare changes in the ABC-I before and after aDIALOG+ and this will be linked to improvements in service users', care workers' or clinicians' ratings on the Clinical Global Impression Scale (global improvement measure). A change indicating that the patient is at least a "minimally improved" will be used as the cut-off score to indicate improvement. We will conduct sensitivity analyses to test different assumptions.

Qualitative data will be analysed using framework analysis to identify themes relating to the barriers and facilitators in implementing aDIALOG+ in clinical and care home settings and aspects of the intervention that need to be refined such as training, supervision and number and frequency of sessions. The focus groups/interviews will be audio-recorded and transcribed. We will use NVIVO to analyse the data using framework analysis to identify relevant themes relating to aspects of the intervention that did not work well and require further modifications, which will inform changes to the intervention. We will also ask clinicians and care workers to complete the NoMAD questionnaire (39) for assessing implementation processes from the perspective of professionals directly involved in the work of implementing complex interventions in healthcare.

Statistical analysis will be carried out on pseudo-anonymised data, and therefore personal identifiable data will not be published. For qualitative interviews, we will remove all

identifiable information from interview transcripts prior to analysis. Participants will be identified using a study ID in publications and we will take care not to present a combination of personal information together that could identify the person (e.g. age, gender, ethnicity).

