## WP2

### *Service Users Inclusion Criteria*

- Aged 18 or over
- Mild or moderate ID based on service records / clinical notes
- Current history of behaviour that challenges (at least one incident of self-injurious behaviour, physical aggression or damage to property in the last 3 months)
- Living in any setting including the family home and supported living/ residential home
- Can provide informed verbal or written consent

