## 12.3 Appendix 2 – WP2 Schedule of Procedures

Procedures	1	2	3	4	5	6	7	8	9	10	11	12	13	14	15	16	17	18
	Jun 25	Jul 25	Aug 25	Sep 25	Oct 25	Nov 25	Dec 25	Jan 26	Feb 26	Mar 26	Apr 26	May 26	Jun 26	Jul 26	Aug 26	Sep 26	Oct 26	Nov 26
Recruitment of clinicians				X	X	X	X											
Clinician training in aDIALOG+				X	X	X	X											
Recruitment of service users					X	X	X	X	X									
Baseline data collection					X	X	X	X	X									
Delivery of aDIALOG+ intervention					X	X	X	X	X	X	X	X	X	X	X			
Follow up											X	X	X	X	X	X		
Stakeholder interviews											X	X	X	X	X	X		
Data analysis																	X	X

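### The CGI-I is described as rating change caused by the intervention, yet it anchors an MCID for ABC-I change from any cause

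*Protocol*

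**What the plan says.** All references are to the protocol.

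- **Design.** WP2: "We will conduct a single arm, uncontrolled, feasibility study of aDIALOG+ delivered by new (haven't participated in other work packages) clinicians". WP3: "We will conduct a single arm, uncontrolled study of aDIALOG+ delivered by new". On timing, section 5 states: "Assessments will be conducted at baseline and post intervention (6 months".
- **Anchor.** Section 5, Outcomes in service users, vi. Global improvement, gives the purpose of the modified CGI: "We will assess whether there are changes in behaviour and functioning as a result of the intervention (at 6 months". The improvement rating runs from 1 (very much improved) to 7 (very much worse). It is made by the person delivering the sessions, the service user and the participant carer.
- **Use of the anchor.** Section 5, Data Storage and Analysis, says of the MCID: "we will compare changes in the ABC-I before and after aDIALOG"+, to be linked to CGI-I improvement. The cut-off is a rating of at least minimally improved, and sensitivity analyses under different assumptions are promised.
- **Objective served.** Section 4.1, secondary objective 6, is to establish the MCID for the ABC-I.
- **Other sources of change.** The WP2 baseline form records prescribed medication and psychosocial interventions such as positive behavioural support. The service use inventory covers contacts and medication over the preceding six months. No section asks for other care to be held constant. Entry to WP2 and WP3 requires "at least one incident of self-injurious behaviour, physical aggression or damage to property in the last 3 months".

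**The concern.** An anchor-based MCID asks how large a score change goes with a change that a rater recognises as small but worthwhile. It needs the anchor and the score to reflect the same change. It does not need that change to have been caused by the treatment, so the attribution clause adds nothing to the MCID.

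The clause can do harm in two ways. Someone whose irritability falls after a medication review should, under the stated purpose, be rated as unchanged by aDIALOG+; that person then sits in the unchanged group with a large ABC-I fall. Conversely, a clinician or care worker who ran the sessions may credit them with any improvement. Raters could then be answering different questions about the same person.

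Secondary objective 6 is at stake. The fault would arise when the rating is made, so an analysis plan could not undo it.

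**Working it through.** The protocol states no MCID figure, so there is nothing to reproduce. The check sets the two definitions side by side and then asks whether the direction of any distortion can be known.

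**Step 1: what each quantity contains.**

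| Quantity | Where defined | Content |
|---|---|---|
| ABC-I change | Data Storage and Analysis | 6-month score against baseline: aDIALOG+, other care, natural course and measurement error together |
| CGI-I rating | vi. Global improvement | By its stated purpose, only the part attributed to aDIALOG+ |

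With no control group, and with other care continuing, a rater has no comparison from which to separate the attributed part.

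**Step 2: does the direction of the distortion follow from the text?** Two illustrations follow. Every input in them is assumed; they test direction only and are not evidence of size in this study.

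*Illustration A: some improvers credit another cause.* Assume 35 improvers with mean ABC-I improvement 8 and 35 unchanged with mean 0. A fraction f of the improvers is rated unchanged.
- Unchanged-group mean = 8 × 35f / (35 + 35f).
- f = 0.2: 56/42 = 1.33, so improved minus unchanged = 8 − 1.33 = 6.67.
- f = 0.4: 112/49 = 2.29, so the difference = 8 − 2.29 = 5.71.
- The mean among those still rated improved stays at 8.

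Here the difference between groups falls, while the improved-group mean does not move.

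*Illustration B: everyone has the same non-specific improvement b, which raters discount.* This is a simulation of 400,000 persons in SD units with no treatment effect. The SD of person-specific change is 0.8, of ABC-I error 0.4 and of rating error 0.5. Minimally improved means a latent rating between 0.3 and 0.8; unchanged means within ±0.3.

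| b | Minimally improved, overall-change anchor | Minimally improved, attribution anchor | Unchanged, attribution anchor | Difference, attribution anchor |
|---|---|---|---|---|
| 0.10 | 0.41 | 0.49 | 0.10 | 0.39 |
| 0.25 | 0.46 | 0.64 | 0.25 | 0.39 |
| 0.40 | 0.50 | 0.78 | 0.40 | 0.38 |

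With the overall-change anchor the difference is 0.38 for every b. Here the improved-group mean is inflated, while the difference between groups is essentially untouched, because the attribution anchor shifts both group means by about b.

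**Step 3: reading the two together.** A lowers the between-group difference and leaves the within-group mean alone; B raises the within-group mean and leaves the difference alone. The protocol does not say which of these sets the MCID. Sign and size are therefore undetermined. An instruction to rate overall change removes the cause in both cases. Reporting the unchanged group's ABC-I change shows the reader how much change came with a rating of no change.

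**The case against.** **The rater's question is not shown.** The Global improvement text gives the study's purpose for a modified instrument, not the item wording. The 1-to-7 labels carry no attribution, and the MCID cut-off is phrased as the patient's improvement. The form may already ask about overall change. This stands: the mismatch is conditional on raters being instructed as the purpose reads. If the form is neutral, the protocol text should be brought into line with it.

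**The estimator belongs in the analysis plan, and sensitivity analyses are promised.** The first part stands, and no fault is found with leaving the estimator open. But neither provision can turn an attribution answer into an overall-change answer after collection.

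**A reader might infer that season confounds the whole pre-post comparison.** The WP2 and WP3 schedules put "Baseline data collection" in October 2025 to February 2026 and follow-up in April to September 2026, with no shared calendar month. The documents do not support taking this further. Nothing in them says that these outcomes vary by season, and any six-month interval moves each person half a year along the calendar.

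**A reader might also infer that the protocol is set to report natural settling as benefit.** It is not. It calls both studies uncontrolled, makes feasibility outcomes the main focus and only explores score changes. Secondary objective 3 speaks of completion and changes without attribution. Entry needs only one incident in three months and is not based on the ABC-I score, so the extent of regression to the mean is unknown. No disclaimer in the objectives or the analysis section is called for.

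**Conclusion.** The point holds in a limited form. As written, the purpose given for the CGI-I does not match its use as anchor for all-cause ABC-I change, and following it would weaken the MCID of secondary objective 6. The primary feasibility aims are unaffected.

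No size can be given. The distortion depends on how many people change for other reasons, how raters assign cause and which estimator is used, and the protocol supplies none of these. The conclusion assumes that raters would be guided by the stated purpose. It does not rest on any seasonal effect or on any claim of efficacy by the protocol. This is a low-cost improvement to make before CGI-I ratings are collected, not an error in a stated figure.

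**What to change.** 1. In section 5, vi. Global improvement, delete the six-word attribution clause that stands between the word functioning and the bracketed time point.
2. Add one instruction to that item and to the modified CGI-I form, for all raters (the person delivering the sessions, the service user and the carer): rate overall change in the person since the baseline visit, whatever its cause.
3. In the MCID paragraph of Data Storage and Analysis, state that ABC-I change in the group rated as having no change will be reported beside that in the minimally improved group.

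Cost: a few words of protocol text, one line on a form and one extra row in a results table. No added visits, measures or participants. The CGI-I would no longer be presented as a measure of change due to aDIALOG+, which an uncontrolled design could not establish in any case.

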## Outcomes in participant carers

### i. Psychological distress

Paid and family carer distress will be measured with the Kessler Psychological Distress Scale - K6 (47).

## Health economics

The feasibility of collecting health economic data: The ease of completing the following measures and response rates will be assessed:

### i. Health Related Quality of Life for service users

Changes in health-related quality of life in participants with ID will be assessed using the EuroQol Five Dimensions - Learning Disability version, a recently developed, modified version of the EQ-5D-3L (48, 49), which will be completed with service users. A proxy version of the EQ-5D-5L (50) will also be completed by participant carers.

### ii. Health Related Quality of Life for participant carers

Health related quality of life for paid/family carers will be measured using the EQ-5D-5L (50).

### iii. Service use

Information about health and social care contacts and medication in the preceding six months will be collected using a modified version of the Client Services Receipt Inventory (CSRI) (51). The CSRI has been used in previous economic evaluations in people with ID and will be adapted for use in this study (52). The number and duration of contacts with primary care, professionals within community ID services (e.g. psychiatrists, nurses, social workers), secondary care (outpatient, Accident and Emergency visits and hospital admissions), day services, medication, paid and unpaid carer input and contacts with criminal justice system, will be collected. All measures will be administered with participant carers but we will also explore the feasibility of collecting information using electronic patient records.

### iv. Treatment costs

We will collect information on the costs of delivering the intervention within clinical services and care homes (e.g. staff time, room bookings, other resources use).

**Table 3: ICONIC WP2 Feasibility screening and data collection schedule**

	Completed by	Storage	Pre-consent	Consent	Baseline	6-month follow-up	Ongoing or during intervention
Clinicians screened for eligibility	RT / CSO	DSH	x				

Clinicians consent form	C / RT / CSO	LC / DB		x			
Clinicians socio-demographic form	C / RT / CSO	DSH			x		
Service users and participant carers screened for eligibility	C	DSH	x				
Service users and participant carers consent form	SU / PC / RT / CSO	LC / DB		x			
Service users socio-demographic and baseline questionnaire	RT / CSO / SU / PC	LC / DB			x		
Participant carers socio-demographic and baseline questionnaire	PC / RT / CSO	LC / DB			x		
aDIALOG+ app data	SU / C / PC	ET					x
Video/audio recordings of sessions and checklists	SU / C / PC	DSH					x
Participant withdrawal CRF	RT / CSO / C / PC / SU	LC / DB					x
SAE CRF	RT / CSO / C / PC / SU	LC / DB					x
Service user 6-month follow up questionnaire	RT / CSO / SU / PC	LC / DB				x	

Participant carer 6-month follow up questionnaire	PC / RT / CSO	LC / DB				x	
Focus group / interview audio recordings and transcripts	SU / C / PC / RT / CSO / TC	DSH				x	
NoMAD questionnaires	C / RT / CSO	DSH				x	
Treatment costs data	C / RT / CSO	DSH				x	

Key: C = clinician; CSO = clinical studies officer; DB = database; DSH = data safe haven; ET = encrypted tablet; LC = (locked cabinet on ELFT property); PC = participant carer; RT = research team; SU = service user; TC = transcription company
							

#### 4. Work package 3: A feasibility study of aDIALOG+ in care homes

Care workers will identify eligible service users and approach them about possibly taking part. If service users are interested, their details will be passed to the research team, who will contact the potential participant, provide an information sheet, and assess their eligibility and capacity to consent. This will be followed by the baseline assessment, which will include demographic and clinical data as described above for service users. For care workers, we will collect demographic data on gender, age, ethnicity, level of education, how many years they have worked in the care home and how many years' experience they have working with people with ID. We will collect information about the care home from service managers (e.g. number of service users and staff employed). Service users will complete the outcome measures (at baseline and 6 months) described above. Informant outcome measures will be completed by the service user's main key worker. We will record the number of care homes, care workers and eligible service users who were approached and agreed to take part. We will also record the number of care workers and service users who dropped out of the study and reasons, and the number of participants that complete the follow-up assessment. We will assess the number of sessions of aDIALOG+ completed by each service user and we will review 20% of the action plans, which will be rated for quality using a fidelity checklist. All the sessions will be audiotaped where possible (and videotaped using Microsoft Teams if possible) and 20% of the recordings for each care worker will be selected randomly and rated using a fidelity checklist to identify the extent to which the intervention was delivered as intended. Acceptability will be assessed by carrying out focus groups at five care homes (at least ten care workers) and interviews with 10 service users. We will purposively select service users based on the number of sessions completed (as above) and a range of care homes will be selected based on the type of care home (supported living/ residential) and size (number of service users). Interviews/ focus groups will be audio-taped and transcribed. We will also ask care workers to complete the NoMAD questionnaire (39) for assessing implementation processes from the perspective of professionals directly involved in the work of implementing complex interventions in healthcare.

